4.4.2. Discontinuation of Investigational Product

Subjects must discontinue investigational product for any of the following reasons:

- Sponsor request, for reasons such as significant protocol deviation (and after discussion with the investigator).
- Study is terminated by the Sponsor.
- Subject meets PML discontinuation criteria (see [Appendix 4](#)).
- Subject develops any other serious opportunistic or atypical infection.
- Subject meets liver chemistry stopping criteria (see [Appendix 3](#)).
- Subject initiates treatment with a prohibited PV disease-modifying drug.
- Subject becomes pregnant.
- Subject experiences a serious or life-threatening cardiac arrhythmia.

Any subject who discontinues from the Treatment Period should complete an Early Withdrawal Visit and transition into the Individualized Follow-up Period for important safety monitoring (as applicable; see Section 3.1.3), unless he/she meets a criterion for mandatory withdrawal from the study (see Section 4.4.3).

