9.3. Assessment Windows

9.3.1. Study Day

When study day is used for display or in comparisons, the following algorithm will be used:

- study day = date of assessment - date of first dose + 1, if date of assessment ≥ first dose date
- study day = date of assessment - date of first dose, if date of assessment < first dose date.

Note that the date of first dose is Day 1 and the day before the date of first dose is Day -1 (there is no Day 0).

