9.3.3. Visit Slotting Algorithm

For all safety and efficacy parameters to be summarized or analyzed by visit, data records will be slotted to one of the protocol specified visits using the following algorithm

- Determine the therapy period and study day for all records using the algorithms from Section 9.3.1 and Section 9.3.2.
- For all records (including unscheduled visit records, early withdrawal records and repeat visit records), use the therapy period and study day determined above with the slotting intervals in the analysis visit window table below to slot the record to the appropriate analysis visit.
 - For records determined to be during the pre-therapy period, the analysis visits will be based on the nominal visits recorded in the eCRF. The Baseline analysis visit will be assigned based on the study day slotting intervals as shown in the table below.
 - For records determined to be during the on-therapy period, use the study day with the slotting intervals in the table below to assign the records to the appropriate on-therapy analysis visit.
 - For records determined to be during the follow-up period, use the study day with the slotting intervals in the table below to assign the records to the appropriate follow-up period analysis visit.
 - For records determined to be during the individualized follow-up period, use the study day with the slotting intervals in the table below to assign the records to the appropriate individualized follow-up period analysis visit.

Table 9-1 Analysis Visit Windows

Scheduled Visit	Target Study Day of Visit	Slotting Intervals
Screening	-84 to -4	Not applicable
Baseline (Week 0)	1	-3 to 1 days
Week 2	15	2 to 22 days
Week 4	29	23 to 36 days
Week 6	43	37 to 50 days
Week 8	57	51 to 64 days
Week 10	71	65 to 78 days
Week 12	85	79 to 92 days
Week 14	99	93 to 106 days
Week 16	113	107 to 120 days
Week 18	127	121 to 134 days

Scheduled Visit	Target Study Day of Visit	Slotting Intervals
Week 20	141	135 to 148 days
Week 22	155	149 to 162 days
Week 24	169	163 to 176 days
Week 28	190	177 to 204 days
Week 32	218	205 to 232 days
Week 36	246	233 to 260 days
Week 40	274	261 to 288 days
Week 44	302	289 to 316 days
Week 48	330	317 to 344 days
Week 52	358	345 to 372 days
Week 56 *	386	373 to 400 days
Week 60** (End of Core Study Period) Subject has completed.	414	401 to 428 days

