* Week 56 is the end of treatment visit for those subjects completing the study per protocol. For subjects who withdraw early from active treatment, the end of treatment visit will be assigned to an analysis visit based on the visit slotting algorithm using study day and therapy period.

** Week 60 is the follow-up visit for those subjects completing the study per protocol. Subjects completing the study and meeting all entry criteria will be offered the option to participate in an extension study, which will start after completion of the Week 60 visit.

For parameters that were not scheduled to be collected at all visits, yet values are available, the visit intervals defined in the table above will be used to slot records. As previously noted for the baseline record, the last non-missing value before the start of treatment will be used for analysis. For post-baseline records, for parameters collected multiple times within a slotting interval, the assessment taken closest to the target study day will be used for analysis/summarization.

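### SAP Table 9-1 sets all nine visit targets from Week 28 to Week 60 seven days too early, so late, unscheduled and early-withdrawal records can be summarised under the wrong visit

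*SAP*

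**What the plan says.** SAP Section 9.3.1 fixes the study-day origin: "Note that the date of first dose is Day 1", and there is no Day 0. SAP Section 9.3.3 then slots all post-baseline records by therapy period and study day, including unscheduled, repeat and early-withdrawal records. Table 9-1 supplies the target days and windows. The rows where the pattern changes are:

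- Week 24: target 169, window "163 to 176 days"
- Week 28: target 190, window "177 to 204 days"
- Week 60: target 414, window "401 to 428 days"

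Three rules then apply the table. If several records fall in one window, "the assessment taken closest to the target study day will be used for analysis/summarization". For subjects who stop treatment early, "the end of treatment visit will be assigned to an analysis visit based on the visit slotting algorithm". The same windows also cover sparsely collected measurements: "For parameters that were not scheduled to be collected at all visits, yet values are available", they are slotted in the same way.

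Protocol Section 4.4.2 makes early-withdrawal records an expected part of the data: "Any subject who discontinues from the Treatment Period should complete an Early Withdrawal Visit".

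**The concern.** SAP Section 3 schedules clinic visits every 4 weeks from Week 8 to Week 60, but the table moves only 21 days from Week 24 to Week 28 (169 to 190). Every later row adds 28 days, so the missing week is never recovered.

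The algorithm covers everything summarised by visit: prednisone dose (SAP 10.6), laboratory data (12.6), immunogenicity (12.6.1), vital signs (12.7.1) and, where tabulated by time point, trough concentrations and B-cell counts (14.1, 14.2). Misplacement can arise in four ways.

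1. **Early withdrawal.** These visits are not tied to the ±3-day rule, and usually no later record is there to out-rank them. The trial stopped early with 69 subjects randomised (SAP 4.2 and 5), so they matter here.
2. **A late scheduled visit.** It can drop out of the summary, leaving its own slot empty. If the next visit is missing or does not collect that parameter, the record appears under the wrong visit. In Protocol Table 6-1, as extracted, HAHA, immunoglobulins and trough samples are due at Weeks 24 and 36 but not at 28 or 40.
3. **A late Week 60 visit.** A record on Day 429 or later has no slot. It leaves the by-visit summary and remains only in the listings.
4. **Two records in one window.** The choice between them is made against a wrong target.

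**Working it through.** **Inputs.** Study day = assessment date − first-dose date + 1 (SAP 9.3.1). Visits are 4 weeks apart after Week 24 (SAP 3). Targets and windows are from SAP Table 9-1. The ±3-day visit window is from the note to Protocol Table 6-1.

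**Target day.** Week w is 7w days after first dose, so its study day is 7w + 1. The SAP does not print this formula, but all 13 rows from Week 0 to Week 24 reproduce it (1, 15, 29, …, 169). None of the nine rows from Week 28 to Week 60 does. Counting first dose as Day 0 does not explain the gap, since 7 × 28 = 196, not 190.

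| Week | Printed target | 7w+1 | Printed window | Days slotted one visit late |
|---|---|---|---|---|
| 28 | 190 | 197 | 177–204 | 177–183 |
| 32 | 218 | 225 | 205–232 | 205–211 |
| 36 | 246 | 253 | 233–260 | 233–239 |
| 40 | 274 | 281 | 261–288 | 261–267 |
| 44 | 302 | 309 | 289–316 | 289–295 |
| 48 | 330 | 337 | 317–344 | 317–323 |
| 52 | 358 | 365 | 345–372 | 345–351 |
| 56 | 386 | 393 | 373–400 | 373–379 |
| 60 | 414 | 421 | 401–428 | 401–407 |

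**Window position.** Around the printed targets the windows run −13/+14 (for Week 28, 177 − 190 and 204 − 190). Around the true days they run −20/+7 (177 − 197 and 204 − 197), and the same holds in all nine rows.

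**Days misplaced.** The windows cover 428 − 177 + 1 = 252 days (9 × 28). Seven days in each belong to the previous visit: 9 × 7 = 63, or 63/252 = 25%. Nine of these (183, 211, …, 407) are exact midpoints. The table's 2-weekly rows give midpoints to the earlier visit; for example, Day 36 is 7 days from both Week 4 and Week 6 and goes to Week 4. Without the midpoints the count is 54, or 54/252 = 21%.

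**Check on the printed targets alone.** Days 177, 178 and 179 are 8, 9 and 10 days from 169 and 13, 12 and 11 days from 190, yet they go to Week 28.

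**Early-withdrawal example.** Day 205 is 8 days after true Week 28 (205 − 197) and 20 days before true Week 32 (225 − 205). The table reports it as Week 32.

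**Late-visit rule.** A record d days late (d = 8 to 14) falls in the next visit's window. The next printed target is 28 − 7 = 21 days after the true day, so the record is 21 − d days from it. The next visit, held k days after its own true day, is 7 + k days from that target.

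- k = 0 (next visit on time, 7 days away): d = 8–13 gives 13–8 days, so the late record is dropped. At d = 14 both are 7 days away, and the SAP has no tie rule.
- k = +3 (10 days away): d = 8–10 gives 13–11 days, dropped; d = 11 ties; d = 12–14 gives 9–7 days, so the late record displaces the next visit's own.

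**Two records in one window.** For Week 28, Day 190 is 0 days from the printed target and an on-time Day 197 is 7 days from it, so Day 190 is used. Any extra record on Days 184–196 would win in the same way.

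**The case against.** The arithmetic is not in dispute. The case against rests on consequences.

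- **Punctual visits are safe.** Every visit within ±3 days falls in its own window, and a late scheduled visit causes trouble only from 8 days late, which is a clear deviation. This stands. However, a slotting table exists for off-schedule, unscheduled and withdrawal records, and those are the ones misplaced.
- **No efficacy conclusion is shown to change.** The co-primary endpoints are derived from actual dates (SAP 11.1.1 and 11.1.2), safety data receive no inferential analysis (SAP 12), and listings keep the records. This stands and limits the seriousness.
- **63 includes tie days, and the midpoint rule is inferred.** True; 54 is the strict count. The tie convention is nevertheless the one the table's own 2-weekly rows follow.
- **The Day 205 example ignores therapy period.** A subject last dosed on Day 169 leaves the on-therapy period after Day 197 (169 + 28), so Day 205 is on-therapy only if the last dose was on Day 177 or later. But Section 9.3.3 sends follow-up records to the same table, which has no other rows for them, so the Day 205 record still meets the Week 32 interval.
- **Any finite last window excludes late Week 60 records.** True. The shift makes the cut-off 7 days earlier than the printed +14 days would otherwise give.
- **Withdrawal dates may cluster at dosing visits.** Possible; the documents give no distribution.

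**Conclusion.** The table is wrong as written. Nine of its 21 post-baseline targets are each 7 days low under the SAP's own study-day rule. A quarter of the days from 177 to 428 (21% without midpoints) are assigned one visit late, and Days 429–435 have no slot although they lie within 14 days of true Week 60.

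If early-withdrawal and unscheduled records after Day 176 were spread evenly over those days, about 1 in 4 would be misplaced. Even spread is an assumption, and the true share could be lower or higher.

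The damage is confined to descriptive by-visit summaries. The correction should be made, but the co-primary results do not depend on it.

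**What to change.** Replace the nine targets with 197, 225, 253, 281, 309, 337, 365, 393 and 421. Use midpoint windows, with ties to the earlier visit:

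- Week 24: 163–183
- Week 28: 184–211
- Week 32: 212–239
- Week 36: 240–267
- Week 40: 268–295
- Week 44: 296–323
- Week 48: 324–351
- Week 52: 352–379
- Week 56: 380–407
- Week 60: from 408

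An upper limit of 435 for Week 60 would keep the printed +14 days (421 + 14). The documents do not give this limit, so it is an assumption for the sponsor to confirm. The SAP should also state the tie rule and say how Week 60 records beyond the limit are handled.

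The cost is one SAP table and the matching program lookup. Data collection, trial conduct and the co-primary analyses are unchanged.

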10. STUDY POPULATION

10.1. Disposition of Subjects

The number of subjects screened and the number of screen failures with primary reason for screening withdrawal will be summarized for each treatment group and percentages will be based on the number of screened subjects. The subjects within each population (ITT, Per Protocol, Safety, PK and PGx) will be summarized in a separate table for each treatment group and percentages will be based on the number of subjects in the ITT population.

For the core study period (i.e. through the Week 60 visit or early discontinuation), a summary of the number and percentage of subjects randomized, treated, completed core study, discontinued from core study, primary reasons for reason for withdrawal from core period, reason for discontinuation due to protocol-defined stopping criteria and subjects who entered open-label extension will be summarized for each treatment group. Percentages will be based on the number of subjects in the ITT population.

A subject will be determined to have completed the core study period if they receive treatment with study medication through Week 56 and complete the Wk 60 Follow-up visit. Percentages will be based on the number of subjects in the ITT population.

The number and percentage of subjects who entered the Individualized Follow-up Period, completed the Individualized Follow-up Period and criterion upon which completion was based, discontinued from the Individualized Follow-up Period and the reason for discontinuation will be summarized for each treatment group. Percentages will be based on the number of subjects in the ITT population.

A summary of subjects randomized by analysis region, country, and site will also be provided by treatment group for the ITT population.

Screening failure details will be presented in a data listing for all subjects who were screening failures. Subject disposition data for the core study period and for the Individualized Follow-up Period and subject completion of Individualized Follow-up Period visits will be presented in data listings for the ITT population.

10.2. Protocol Deviations

Subjects who fail to fulfill any of the inclusion/exclusion criteria will be tabulated for each treatment group and listed for each subject in the ITT population.

Protocol deviations will be tracked by the clinical team on an on-going basis through the completion the individualized follow-up period (or early withdrawal from the study) for all subjects and will be listed by subject. The number and percentage of subjects with any protocol deviation and the number and percentage of subjects experiencing each protocol deviation category will be summarized for the ITT population.

Specific criteria for what constitutes a major protocol deviation (i.e. causing exclusion from the Per Protocol population) will be identified by the study team prior to study unblinding. The following criteria may be considered:

- Not meeting key inclusion/exclusion criteria
- Withdrawal criteria met but subject not withdrawn
- Taking prohibited concomitant medications
- Not being compliant with the study medication dosing schedule

Please refer to Section 6.3 for a discussion of protocol deviations as they pertain to the PP population.

The analysis sets and severity codes used in the trial programming are listed in below Table, which includes the analysis set codes 1-5 and the severity codes 0, 1, 5, 8 and 49 for the double-blind treatment period.

Table 10-1 The analysis populations and severity codes

Analysis set codes	Deviation Severity Codes		
1 = Screening Population 2 = Intent-to treat Population 3 = Per protocol Population 4 = Safety Population	0 = Exclude patient from all efficacy analyses 1 = Exclude patient from per-protocol analysis 8 = Exclude patient from all analyses		
	Deviation Severity Codes		
Analysis set (code)	0	1	8
Screening Population (1)	Yes	Yes	No
Intent-to-Treat population (2)	No	Yes	No
Per Protocol Population (3)	No	No	No
Safety Population (4)	Yes	Yes	No

Note: 'Yes' means include in the analysis population, 'No' means exclude from the analysis population.

The number and percentage of subjects with any major protocol deviation and the number and percentage of subjects experiencing each major protocol deviation category will be summarized for the ITT population. Major protocol deviations with deviation category and severity codes will be identified in the protocol deviations listing presented by subject for the ITT population.

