6.2. Intent-to-Treat (ITT) Population

The ITT population will include all randomized subjects regardless of whether or not they received a dose of investigational product (IP). This will be the primary population used for the efficacy analyses.

In the event of a discrepancy between the treatment assigned at randomization and the actual treatment received, subjects will be analyzed according to the treatment to which they were randomized.

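### SAP Table 10-1 drops deviation codes 0 and 8 from ITT and code 8 from Safety, against the plan's own definitions of those sets

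*SAP*

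**What the plan says.** **Definitions.** SAP 6.2 states: "The ITT population will include all randomized subjects regardless of whether or not they received a dose of investigational product (IP". Protocol 8.3.1 likewise takes ITT as all randomised subjects. Safety, in Protocol 8.3.1 and SAP 6.4, is every randomised subject given at least one dose. The only further rule in SAP 6.2 and 6.4 concerns the arm in which a wrongly treated subject is counted, not whether the subject is counted.

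**Deviations in the text.** SAP 6.3 says that rules fixed before unblinding will decide which deviations remove a subject from the Per Protocol (PP) set. SAP 10.2 describes a major deviation the same way: "i.e. causing exclusion from the Per Protocol population".

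**Deviations in the table.** SAP Table 10-1 defines severity code 0 as "0 = Exclude patient from all efficacy analyses" and code 8 as "8 = Exclude patient from all analyses"; code 1 removes a subject from the per-protocol analysis only. The grid below the labels gives a Yes or No for each set and code, and its note explains the negative entry: "No' means exclude from the analysis population".

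**Use of the sets.** SAP 11 runs the co-primary and secondary efficacy analyses on ITT. SAP 12 runs safety on the Section 6.4 set.

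**Visibility.** One sentence in SAP 10.2 has deviations tracked for all subjects and listed by subject. A later one reads: "Major protocol deviations with deviation category and severity codes will be identified in the protocol deviations listing presented by subject for the ITT population". SAP 10.1 adds a count table: "The subjects within each population (ITT, Per Protocol, Safety, PK and PGx) will be summarized in a separate table for each treatment group".

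**The concern.** The plan gives two rules for who belongs to ITT and two for who belongs to Safety. One is in the definitions that the analysis sections rely on. The other is in the table that the programs are said to follow. A programmer working from Section 6 and one working from Table 10-1 would build different sets as soon as a randomised subject is given code 0 or 8.

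At stake is the population for both co-primary endpoints and, for code 8, the completeness of the safety tables. The SAP gives no criteria for assigning either code, so a reader cannot tell which subjects the table is meant to remove. The requirement to fix the rules before unblinding is written for PP exclusions and does not clearly reach exclusions from ITT or Safety.

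**Working it through.** **1. Table against definitions.**

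| Set | Definition in the text | Code 0 | Code 1 | Code 8 | Conflict |
|---|---|---|---|---|---|
| ITT | all randomised (Protocol 8.3.1, SAP 6.2) | No | Yes | No | codes 0 and 8 |
| Safety | randomised, at least one dose (Protocol 8.3.1, SAP 6.4) | Yes | Yes | No | code 8 |
| PP | ITT without major deviations (SAP 6.3) | No | No | No | none |

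The code labels agree with the grid entries, so the conflict does not come from a table broken in text extraction. Code 1 is the only code that agrees with the definitions in every row.

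**2. Size of the sets.** Input: 69 randomised (SAP 5). Let a be the number of randomised subjects holding code 0 or 8, D the number dosed, and b the number of dosed subjects holding code 8.
- Text: ITT = 69; Safety = D.
- Table: ITT = 69 − a; Safety = D − b.
- The documents give neither a nor b. If both are zero, the two rules coincide.
- Each subject removed from ITT is 1/69 = 1.4%; three would be 3/69 = 4.3%.

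**3. Knock-on for the PP rule (hypothetical counts).** SAP 6.3 and 11 analyse PP only if it is between 50% and 95% of ITT. Suppose 65 subjects are in PP. With ITT as written, 65/69 = 94.2%, so PP is analysed. If one of the four excluded subjects holds code 0, the table gives 65/68 = 95.6%, and PP is not analysed.

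**4. Sensitivity if exclusions were related to outcome (illustration only).** Assumptions: a 34 versus 35 split, with 27 and 19 responders, close to the 80% and 54% in Protocol 8.2.1. The test is an unadjusted pooled two-proportion test, z = d / √[p(1−p)(1/n₁ + 1/n₀)], not the planned stratified log-rank test. Non-responders are removed from the ofatumumab arm only.
- None removed: 27/34 − 19/35 = 25.1 points, z = 2.21, two-sided p = 0.027.
- One removed: 27/33 − 19/35 = 27.5 points, p = 0.015.
- Two removed: 27/32 − 19/35 = 30.1 points, z = 2.65, p = 0.008.

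This is a deliberately one-sided case. It shows what a few selected exclusions can do in a set of this size, and says nothing about what happened in the trial.

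**The case against.** The best case against is that Section 6 is explicit and governs. SAP 12 points to Section 6.4 by number, SAP 11 names ITT, and no text assigns code 0 or 8 to any class of deviation. The inconsistency is therefore latent. In addition, the trial stopped early, the multiplicity procedure was dropped and p-values are nominal (SAP 1, 8.3 and 11.1.3), so no controlled confirmatory claim rests on the table. All of this stands, and it limits the weight of the point. It does not remove the contradiction, because the table is offered as what the programs implement and nothing says that Section 6 overrides it.

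Four stronger readings are tempting and are not supported:

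- **Subjects were removed, or results were biased.** The documents do not show any subject with code 0 or 8.
- **Removed subjects would be untraceable.** The severity-code listing is tied to ITT, but SAP 10.2 also lists deviations by subject without that limit, and SAP 3.1 provides a randomisation listing without restriction. A removed subject could be found by comparing listings. What remains is that the two sentences in SAP 10.2 differ in scope.
- **The Safety entry of Yes for code 0 proves that such subjects were randomised and dosed.** The grid can be read as a filter applied after the Section 6 definitions: an undosed subject with code 1 also shows Yes for Safety. The entry does not settle what code 0 means.
- **Some codes are undefined.** The lead-in announces a table "which includes the analysis set codes 1-5 and the severity codes 0, 1, 5, 8 and 49", and the text available here shows fewer. Rows may have been lost in extraction, so this is not counted as a fault.

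**Conclusion.** The contradiction is real and explicit. Table 10-1 excludes randomised subjects from ITT under codes 0 and 8, and dosed subjects from Safety under code 8, while the protocol and SAP definitions allow no such exclusion. This rests on the table labels, grid and note as they appear, and on the absence of any deviation exception in Protocol 8.3.1, SAP 6.2 and SAP 6.4.

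The effect is conditional. It is nil if no randomised subject holds code 0 or 8. Otherwise each such subject changes the co-primary population by 1.4% of 69, and the effect on the result depends on who they are, which the documents do not tell. The table should be corrected because the conflict touches the primary and safety sets and is cheap to remove, not because harm has been demonstrated.

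**What to change.** 1. In Table 10-1, set the ITT row to Yes under every code for randomised subjects and the Safety row to Yes under every code for dosed subjects. Relabel or delete codes 0 and 8 so that deviations act on the PP set only, and match the program flags.
2. If a narrow exception is intended, write it with its criteria into SAP 6.2 and 6.4, list each subject affected, and also report the analysis of all randomised subjects.
3. Reconcile the two listing sentences in SAP 10.2 so that the listing showing severity codes covers all randomised subjects.

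The cost is one table correction, one sentence on the listing and a check of the flags. No new data are needed.
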